PRINCIPAL INVESTIGATOR (LAST, FIRST, MIDDLE): [name]

programs. In contrast, one organization, Nueva Vida, currently offers the proposed PCI with its innovative format. Nueva Vida has observed specific benefits to both survivors and caregivers after participating in their patient-caregiver program. *These observations led Nueva Vida to ask [name] (PI) to partner on the present submission to formally evaluate the program.* Nueva Vida and the other three partners are interested in learning which strategies provide the most benefit to Latina survivors and their caregivers. Each day, the patient navigators, promotoras (health educators) and trained mental health professionals make recommendations to Latina survivors and their family members about different options for support. Study findings will provide evidence about whether inclusion of caregivers significantly improves patient-centered outcomes of QOL, communication and satisfaction with care. We will also explore the impact of the intervention on adherence to guideline-concurrent follow-up care for survivors. The evidence gained from the proposed study could impact the types of services offered by each of these organizations (and other organizations like them). If successful, ***study outcomes could to lead to use of an empirically-based intervention for the thousands of Latina survivors who receive services from our four partners.***

Prospects for Prompt Dissemination and Adoption of Findings into Practice. Our study team is excited about the potential benefits of PCI and prospects for dissemination of study findings. We have several strategies for dissemination of study findings that we will explore and discuss further over the course of the study (see Section 8, Project Plan and Time Table and the Stakeholder and Patient Engagement Plan in People and Places). Below we describe some of these options.

First, we will disseminate study findings to study participants and to other families facing cancer who are served by the four partner organizations. Together, our four partners provide services and information to over 18,000 people annually, of which over 8,000 are Latino. We will disseminate study results through each of the organization's websites, newsletters and other print materials. Likewise, Gilda's Club New York City will help our team share study results with other Clubhouses across the country (see Letter of Support).

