Choice of Comparators. We will compare a patient-caregiver intervention (PCI) to usual care. We elected to compare PCI to usual care for several reasons. First, PCI is an intervention developed by and for Latina survivors. It is being successfully used at Nueva Vida, a community organization that provides care and support to Latinas with breast cancer in the Washington, DC metropolitan area (see Appendix A for sample materials). Second, no other organizations or clinics are currently using the PCI intervention. Third, no research to date has evaluated a patient and caregiver intervention in an ethnically diverse sample of cancer survivors and caregivers.³⁴ Fourth, our comparator of usual care is reasonable given that the other community organizations involved all provide support programs, navigation and educational initiatives for Latina survivors.²²⁻²⁴ If PCI performs better than usual care at improving key patient-centered outcomes, then community organizations and other stakeholder groups can adopt PCI into practice. We will carefully monitor adherence to both PCI and attendance at any services available through usual care. We will include both intent-to-treat and “per protocol” analyses to investigate the impact of session attendance on study outcomes (see Analytic Methods). Below we describe the intervention and usual care.

Refinement of Intervention Materials. We will refine the PCI intervention protocols/manuals based on in-depth interviews with 10 Latina survivors-caregiver dyads (see Appendix B). The interviews will allow us to refine the intervention for Latinas from different geographic regions (DC, NY or CA) and from different countries of origin (see Table 5). PCI is based on our current materials (Appendix A), experience,^{16-18,53,65,90,91} formative work and our conceptual models.^{12,14,62} Team and advisory board members will provide further input on ways to refine PCI, reflecting perspectives from patients, caregivers, providers (clinical and counseling psychology, medical oncology, breast surgery, internal medicine, social work), researchers (health services, public health, disparities) and stakeholders (patient advocates, community partners).

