Data Analyses. Aim 1. *To evaluate the impact of the PCI intervention on Latina survivors' and caregivers' QOL.* **H₁:** Survivors and caregivers in PCI will report higher QOL compared to those assigned to UC. Aim 1 analyses will be performed separately for the Latina survivors and carriers. With 50 Latina survivors (and caregivers) per arm we will have 84% power to detect a clinically significant difference in QOL of 6 points (0.6 SD on PROMIS QOL measures) at a significance level of 0.05. Changes of PROMIS of 5 points or more are clinically significant.⁶⁰ We will use a mixed effects model to compare the two arms with respect to QOL immediately post intervention and at 6-months, adjusting for statistically significant (at the 0.10 level) predictors of QOL identified in bivariate analyses. In addition to this intent-to-treat analysis, we will perform a "per protocol" comparison of intervention completers vs. non-completers (defined as attending fewer than five sessions). We will use a mixed effects model to compare these groups on QOL immediately post intervention and at 6-months, controlling for potential confounders associated with both intervention completion and QOL in bivariate analyses. As we expect the sample of Latina survivors and their caregivers in the present study to be representative of the over 8,000 individuals who seek services or information from the community organizations involved in the study, our findings should generalize to thousands of Latina women in the Washington DC, New York City and San Jose, CA areas. For the survivors we will also explore whether geographic region (DC, NY or CA), nationality (U.S. born vs. immigrant) or region of origin (e.g., Central America, South American) modifies the effect of the intervention on QOL. We will also explore whether caregiver gender impacts the effect of the intervention on QOL.

Aim 2. *To identify mediators of the PCI intervention on QOL.* **H₂:** Consistent with our experience and theoretical models, changes in QOL will be due to improved communication self-efficacy, improved social support and decreased distress among PCI participants vs. UC participants. Aim 2 analyses will be performed separately for the Latina survivors and caregivers. We will use the product of coefficients method to assess

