mediation effects at 6-months.¹¹⁹ We will use linear regression models to estimate the coefficients relating each mediating variable (self-efficacy, social support, and distress) to QOL at 6-months, and also the coefficients relating the intervention to each mediating variable. We will calculate the mediated effects as the products of corresponding coefficients and we will construct 95% confidence intervals according to the methods described by MacKinnon et al.¹¹⁹ With 50 subjects per arm we will have 80% power to detect mediation effects of moderate size (with coefficient parameters of 0.39 or more) for each mediator.¹¹⁹

Aim 3. To evaluate the impact of the PCI intervention on Latina survivors' satisfaction with their cancer care. **H₃:** Survivors in PCI will report greater satisfaction with their cancer care compared to UC participants. With 50 Latina survivors per arm we will have 96% power to detect a clinically significant difference in satisfaction with care of 8 points (0.75 SD given estimated SD of 12)¹²⁰ at a significance level of 0.05. We will use a mixed effects model to compare the two arms with respect to satisfaction with care immediately post intervention and at 6-months, adjusting for statistically significant (at the 0.10 level) predictors of satisfaction with care identified in bivariate analyses. We will again explore whether the effect of the intervention on satisfaction with care is different for sub-groups of participants (e.g., whether the impact of PCI on satisfaction with care differs by geographic region (e.g., NY,CA) or region of origin (e.g., Central America, South American)).

Exploratory Aim: To explore the impact of the PCI intervention on Latina survivors' adherence to guideline-concurrent care and surveillance. Given the exploratory nature of this aim no formal power calculation was performed. We will use logistic regression models to compare the two arms with respect to the binary outcomes of adherence to guideline-concurrent care (hormonal therapy; chemotherapy) and surveillance (mammogram within 12 months), controlling for the statistically significant (at the 0.05 level) covariates identified in bivariate analyses. We will also perform "per protocol" analyses of completers vs. non-completers similar to those described in Aim 1.

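### The supplementary completer analysis is not a randomised comparison: it groups people by attendance after randomisation, leaves the comparator arm unstated, and screens baseline QOL instead of always adjusting for it

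*Combined protocol and SAP*

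**What the plan says.** Aim 1 (C.2, Data Analyses) compares the randomised arms on QOL at both follow-ups, with 84% power for 6 points. "In addition to this intent-to-treat analysis", it plans an analysis labelled per protocol, a "comparison of intervention completers vs. non-completers (defined as attending fewer than five sessions". This uses a mixed model at the same two visits, "controlling for potential confounders associated with both intervention completion and QOL in bivariate analyses". No significance level is given for that screen, although the covariate rule for the arm comparison states 0.10.

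C.1, Choice of Comparators, gives the purpose of including both intent-to-treat and per-protocol analyses: "to investigate the impact of session attendance on study outcomes". The Exploratory Aim repeats the grouping for guideline adherence, with "analyses of completers vs. non-completers similar to those described in Aim 1".

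The patient-caregiver intervention (PCI) has eight sessions, which start after randomisation. A completer therefore attends five to eight. No section says whether UC participants count as non-completers, and no section plans an attendance analysis that keeps the randomised arms.

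On UC exposure, Choice of Comparators says "no other organizations or clinics are currently using the PCI intervention", and A.2.2 says that "one organization, Nueva Vida, currently offers the proposed PCI with its innovative format". Protection of Human Subjects (1a) opens all normally available partner services to UC dyads. The Usual Care paragraph and Potential Benefits (section 3) offer the combined programme after the 6-month assessment, and Appendix C says UC is not exposed to the manualised sessions. Service use is to be tracked: "We will carefully monitor adherence to both PCI and attendance at any services available through usual care".

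**The concern.** The stated purpose is causal, but attendance is something participants do after assignment. People who come to five or more sessions may differ from those who do not in health, motivation or caregiver availability, and such factors can also affect QOL. The resulting difference can go either way and can appear when PCI does nothing.

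The missing comparator adds a second problem. A contrast within PCI and a contrast that pools UC with PCI non-completers estimate different things. Neither compares PCI completers with comparable UC participants. The choice could also be made after the data are seen.

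The label matters because readers commonly take a per-protocol result as a treatment effect against control among those who adhered. Section A.2.2 says the findings could shape which services the partner organisations offer.

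**Working it through.** **The plan's own figure.** Two-sided t-test, 50 per arm, difference 6, SD 10, alpha 0.05: power 84.4%, matching the stated 84%. This belongs to the arm comparison; no power is stated for the completer contrast.

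**Why the comparator matters.** Assume 70% of 50 PCI participants complete. Within PCI the groups are 35 and 15, and power for 0.6 SD is 48%. With UC pooled they are 35 and 65, and power is 81%.

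**Inputs for bias.** From the documents: SD 10 and 50 per arm. Assumed, because the documents give neither: the completion proportion p, and the correlation r between the tendency to attend and QOL that remains after adjustment. The true PCI effect is set to zero. φ is the standard normal density at the completion cut-point: 0.399, 0.348 and 0.175 for p = 0.5, 0.7 and 0.9.

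**Unmeasured selection.**
- Within PCI: bias = r × SD × φ / [p(1−p)]. At r = 0.1 and p = 0.7 this is 0.1 × 10 × 0.348 / 0.21 = 1.66 points. At p = 0.5 and 0.9 it is 1.60 and 1.95.
- UC pooled: bias = r × SD × φ × [1/p + 1/(2−p)]. At r = 0.1 this is 1.06, 0.76 and 0.35 points for p = 0.5, 0.7 and 0.9.

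**Screening baseline QOL.** Assume it correlates 0.2 with attendance propensity and 0.6 with follow-up QOL, p = 0.7, within PCI. Unadjusted bias is 0.2 × 0.6 × 10 × 0.348 / 0.21 = 1.99 (simulated 1.97). In 8,000 simulated null trials using a single-visit regression, requiring baseline QOL to pass both bivariate tests leaves 1.16 points (screen at 0.05) or 0.84 (0.10). Always adjusting leaves −0.02.

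**Other measured confounders, same setting.**

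| Confounders (each 0.2 with propensity, 0.3 with QOL) | Points left | False positives (nominal 5%) |
|---|---|---|
| One | 0.5–0.7 | about 5% |
| Five, independent, same direction | 2.5–3.4 | 11–18% |
| Five, inter-correlated 0.3 | 0.4–0.95 | 4.6–6.4% |
| Five, inter-correlated 0.5 | 0.1–0.5 | 4.6–4.8% |
| Five, independent, three positive and two negative | 0.6–0.7 | 3.6–4.4% |

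Ranges cover screens at 0.05 and 0.10.

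**Precision of the alternative.** The intent-to-treat 95% half-width is 1.984 × 10 × √(2/50) = 3.97 points. The CACE half-width is about that divided by (PCI uptake − UC uptake). At 70% and 0% it is 3.97/0.7 = 5.7; at 70% and an assumed 10% it is 3.97/0.6 = 6.6.

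**The case against.** The analysis is supplementary, comes after intent-to-treat and is adjusted. QOL, distress and social support are all measured at baseline (Table 4), so important confounders are available. The phrase intervention completers most naturally means people within PCI, and the analysis plan still to be written (Replication of Research Findings, item 7) could say so. All of this is fair, and it limits the weight of the point.

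Four stronger readings are tempting and should not be adopted.
- A reader might infer that non-completers are undefined. They are defined by session count; what is missing is the arm. The selection problem comes from the grouping itself, so naming the arm would not remove it.
- A reader might infer that measured confounding badly inflates false positives. The 11–18% figure needs five independent confounders acting in the same direction. Together these would explain 5 × 0.3² = 45% of QOL variance. Baseline QOL, distress and social support are unlikely to be independent, and correlated confounders leave under 1 point with near-nominal error.
- A reader might infer that UC participants will receive PCI during follow-up. The Usual Care paragraph and Potential Benefits defer the combined programme, and Appendix C excludes exposure. What remains is tension with A.2.2 and Protection of Human Subjects, not evidence of contamination.
- A reader might doubt the main result. The arm comparison does not use attendance at all.

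The objection does not answer three things: the unstated arm, the screening of baseline QOL, and unmeasured selection.

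**Conclusion.** The concern holds in limited form. The completer contrast cannot isolate the impact of attendance, whichever arm supplies the non-completers. With no true effect, it is plausibly off by about 1 to 2 points: 0.8 to 1.2 from screening baseline QOL, and 1.6 to 2.0 within PCI (0.4 to 1.1 with UC pooled) from unmeasured selection at r = 0.1. That is below the plan's 5-point threshold, but large enough to colour a small or null result.

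These sizes rest on assumed completion rates and correlations, on bias in one direction, and on single-visit calculations instead of the planned two-visit mixed model. The design point needs none of those assumptions. Because the analysis is supplementary, this is a change the sponsor should make, not a threat to the trial's primary conclusion.

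**What to change.** **1. If the completer contrast is kept:** state which arm supplies the non-completers, and always adjust the QOL contrast for baseline QOL instead of screening it. Drop the per-protocol label and report the contrast as descriptive and non-randomised. The labelling and reporting apply to the adherence outcomes too.

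**2. Add one CACE analysis of QOL at each follow-up.** Use randomised arm as the instrument and recorded attendance at five or more PCI sessions as uptake, separately for survivors and caregivers. Add one sensitivity analysis with uptake defined as at least one session.

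**3. Record UC attendance at the existing patient-caregiver programme** instead of assuming none. A.2.2 and Protection of Human Subjects (1a) should be reconciled with the Usual Care paragraph, Potential Benefits and Appendix C.

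**Cost.** Steps 1 and 3 need wording in the analysis plan and one extra marker in service records that are already kept. Step 2 uses attendance data already collected and has these drawbacks:
- Its interval is about 1.4 times the intent-to-treat interval at 70% completion (half-width 5.7 against 4.0 points).
- It gives an effect size among compliers, not new evidence of efficacy.
- It assumes attendance below the threshold has no effect. A 3-point effect in every non-completer would overstate the result by 3 × 0.3/0.7 = 1.3 points at 70%; the sensitivity analysis addresses this.
- It assumes the partner's attendance alone has no effect. A 3-point partner-only effect would overstate it by 0.4 to 0.9 points at 70%, depending on how often partners attend together.
- Missing outcomes (125 dyads enrolled, 100 expected at 6 months) must be handled as in the intent-to-treat model.

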	Control for interventionists' differences.	Assess participants' perceptions of interventionists' warmth and credibility via self-report satisfaction questionnaire and provide feedback to interventionists. Include in analyses if appropriate. Monitor participant complaints. Have different co-investigators evaluate session notes and intervention delivery checklists.
	Reduce differences within treatment.	Use treatment manual and handouts for PCI condition.
	Ensure adherence to treatment protocol.	Interventionists will complete a checklist of intervention components delivered after each session for all groups.
	Minimize contamination between conditions.	Emphasize in training sessions the rationale for keeping conditions separate. As survivors and caregivers in the UC condition are not exposed to in any way to manualized group sessions, contamination concerns are lessened. We will track usage of other support programs by all participants.
Monitoring and Improving Receipt of Treatment	Goal	Strategies for Implementation
	Ensure participant comprehension.	Assess skills and functioning at baseline (e.g., self-efficacy for communication, social support, distress). Intervention includes the practice of skills and behavioral strategies within each group session. Have interventionist ask questions/use prompts that ask participants to paraphrase/summarize content. Record interventionists' perceptions of participant understanding after each session.
	Maximize participant ability to use skills.	Measure mediating variables immediately post-intervention and 6-months post intervention. Ask participants to provide feedback on their ability to understand and use materials.
Monitoring and Improving Enactment of Treatment Skills	Goal	Strategies for Implementation
	Ensure participant ability to perform behavioral skills.	Monitor homework completion and engagement in session discussion.

Strategies adapted from recommendations provided in Bellg AJ, Borrelli B, Resnick B, Hecht J, Minicucci DS, Ory M, Ogedegbe G, Orwig D, Ernst D, Czajkowski S, et al. Enhancing treatment fidelity in health behavior change studies: best practices and recommendations from the NIH Behavior Change Consortium. *Health Psychol* 2004;23(5):443-451. PMID:15367063.

PRINCIPAL INVESTIGATOR (LAST, FIRST, MIDDLE): [name]

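### Aim 2 does not fix the mediator's wave, the arm term or baseline adjustment, so a same-interview association at 6 months could be reported as mediation

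*Combined protocol and SAP*

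**What the plan says.** The method is in section C.2, Data Analyses, Aim 2. The plan states "We will use the product of coefficients method to assess" and ends that sentence with "mediation effects at 6-months". For the path from mediator to outcome it gives "linear regression models to estimate the coefficients relating each mediating variable (self-efficacy, social support, and distress) to QOL at 6-months". The other path, from arm to mediator, is a further regression of each mediator on randomised group. The products of corresponding coefficients are the mediated effects, and "we will construct 95% confidence intervals" by a cited method. The hypothesis is about change: "changes in QOL will be due to improved communication self-efficacy, improved social support and decreased distress among PCI participants".

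Four things are not stated for Aim 2: the wave of the mediator, an arm term in the QOL regression, the baseline mediator, and baseline QOL. Aims 1 and 3 each carry a covariate rule; Aim 2 has none. The Randomization paragraph offers to control variables as appropriate, but it concerns factors such as age, time since diagnosis and stage.

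The data for a time-ordered model exist. Table 4 marks QOL, communication self-efficacy, social support and distress at baseline, T1 (immediately after the intervention) and T2 (6 months later). Appendix C repeats the intention: "Measure mediating variables immediately post-intervention and 6-months post intervention". The paragraph on follow-up interviews places QOL and the mediators in the same call.

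**The concern.** Randomisation protects the arm-to-mediator path. It does not protect the mediator-to-QOL path, because nobody is randomised to a level of self-efficacy, support or distress. When both are taken in one telephone call, mood that day and reporting style feed both scores. A lasting disposition feeds both at every call. The overlap is closest for distress: the PROMIS domains that define QOL include anxiety and depression, while distress, measured by the Brief Symptom Inventory, is a mediator.

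A product of coefficients multiplies this association by the arm effect on the mediator. If PCI shifts the mediator, the product can be clearly non-zero although the mediator does nothing to QOL. What is at stake is the answer to H2, and with it any advice on which components of PCI matter. The limitations paragraph in C.2 mentions neither time order nor mediator-outcome confounding.

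**Working it through.** **The plan's own figure.** The plan states: "With 50 subjects per arm we will have 80% power to detect mediation effects of moderate size (with coefficient parameters of 0.39 or more". Take n = 100, a = b = 0.39, unit residual SDs and two-sided 0.05, with both paths required to be significant.

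- Arm scaled to variance 1: noncentrality 0.39 × √100 = 3.9 on each path, 97.1% each, jointly 0.971 × 0.971 = 94%.
- Arm coded 0/1 in equal groups (variance 0.25): 0.39 × √(100 × 0.25) = 1.95 for a, which gives 48.8%; 0.488 × 0.971 = 47%.

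The stated 80% is not reproduced on either scale, and the plan does not say which scale is meant. That is a separate matter. Here it means only that the 80% cannot be carried over to another model.

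**Inputs for the check.** From the documents: 50 per arm, and a PROMIS SD of 10. Assumed, because the documents give no values:

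- PCI shifts the mediator by 0.5 SD at T1 and T2.
- Half the variance of each score is stable over time.
- The stable parts correlate 0.5, and so do the same-call parts (alternative: both 0.3).
- The mediator has no true effect on QOL, and arm has no direct effect.

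**Expected products, by hand (correlations 0.5).**

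- T2 mediator with arm: same-call correlation 0.5 × 0.5 + 0.5 × 0.5 = 0.5. Product 0.5 × 0.5 = 0.25 SD, or 2.5 PROMIS points (simulated 0.249).
- T2 mediator without arm: mediator variance becomes 1 + 0.25 × 0.5² = 1.0625, so b = 0.5/1.0625 = 0.47 and the product is 0.235 (simulated 0.232).
- T1 mediator with arm: only the stable part carries over, b = 0.5 × 0.5 = 0.25, product 0.125 (simulated 0.125).
- T1 mediator with arm and both baselines: b = (0.25 − 0.5 × 0.25)/(1 − 0.5 × 0.5) = 0.125/0.75 = 0.167, product 0.083 (simulated 0.084).

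All four should be zero.

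**False mediation at n = 100** (1,000 replicates, 95% distribution-of-the-product interval excluding zero):

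| Mediator and terms | Correlations 0.5 | Correlations 0.3 |
|---|---|---|
| T2, no arm, no baselines | 71% | 55% |
| T2, arm | 71% | 57% |
| T2, arm, baselines | 82% | 70% |
| T1, arm | 49% | 19% |
| T1, arm, baselines | 30% | 12% |

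**Why arm and baselines do not rescue a T2 mediator.** Its b path is almost always significant, so false mediation occurs about as often as the arm-to-mediator test succeeds. The standard error of that test is 2/√100 = 0.2; 0.5/0.2 = 2.5; Φ(2.5 − 1.96) = 71%. Baselines cut the standard error to 0.2 × √0.75 = 0.173; 0.5/0.173 = 2.89; Φ(2.89 − 1.96) = 82%. The spurious b stays at 0.5 and the a path is estimated more precisely, so the error rate rises.

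**Boundary cases.** If PCI does not move the mediator, the barest model gives 6%. Leaving arm out, with a 0.6 SD direct effect and no correlation between mediator and QOL, moves the rate only from 3% to 8%.

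**Large-sample bias.** With a 0.6 SD shift, 60% stable variance, stable correlation 0.4-0.6 and same-call correlation 0.4-0.5, the concurrent model gives 2.2-3.6 spurious points. The T1 mediator with arm and both baselines gives 0.9-1.2. The plan treats 5 points as clinically significant. Across the simulation settings used, false mediation in the lagged model reaches up to 39%. At the low end, its residual bias with correlations of 0.3 is 0.050 × 10 = 0.5 points.

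**The case against.** The strongest reply is that silence is not exclusion. A reader might infer that the plan leaves arm and baseline values out of the QOL model, or commits to a T2 mediator. The documents do not support that. They fix QOL at 6 months, and a T1 mediator also fits the words. The method is partly delegated to a cited mediation paper that was not available for this check, and the section on replication promises a final protocol and a written analysis plan. All of this stands. It turns the point from a wrong model into an open choice, one that could be made after the data are seen.

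A reader might also infer that mediation will be declared whenever PCI moves a mediator, so that the trial cannot address mechanism at all. The simulations do not show that: the rate is 55-71% under the stated assumptions, not certainty.

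Third, the size follows largely from assumed correlations. With no stable correlation and a same-call correlation of 0.4, the bare concurrent model gives only 0.9-1.4 points. That is fair; the figures show what is plausible and do not predict this trial.

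Finally, the three omissions are not equal. The wave does most of the harm, and asking only for an arm term and baselines would miss the problem.

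**Conclusion.** The point holds as a gap in specification with a realistic consequence. Aim 2 leaves the mediator wave, the arm term and baseline adjustment open, and its natural reading pairs mediator and QOL from one call. If PCI moves the mediator, a same-interview association could then pass as mediation. The rate is roughly 55-71% of trials at n = 100, given an assumed 0.5 SD shift and correlations of 0.3-0.5.

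The lagged model is better but not clean: about 0.5-1.2 spurious points and 12-39% false mediation remain. A reader might infer that lagging settles causality; it does not, because a stable disposition still links the T1 mediator to T2 QOL. The matter is confined to a mechanistic aim. The randomised Aim 1 comparison is untouched.

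**What to change.** Prespecify in Aim 2, separately for survivors and caregivers:

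1. Regress the T1 mediator on arm, baseline mediator, baseline QOL and location.
2. Regress T2 QOL on the T1 mediator, arm, baseline mediator, baseline QOL and location.
3. Take the product of the two paths with the interval already planned. Label any model pairing T2 mediator with T2 QOL as descriptive.
4. Add a sensitivity analysis for mediator-outcome confounding, including a version that also adjusts for T1 QOL, which is already collected. In the large-sample simulation this left between −0.1 and 0.2 points. It belongs in sensitivity because T1 QOL is itself measured after randomisation and may absorb part of a real effect.
5. Word H2 conclusions as consistent with mediation, not as proof of it.

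The cost is analysis wording only, since every variable is collected at all three waves. The lagged path is smaller, so its power is lower, and participants without a T1 interview drop out of a complete-case fit. The stated 80% should be recalculated for these models, with the coefficient scale and arm coding given.

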Secondary Outcomes. (a) **Communication with Providers** will be measured with a validated 15-item measure.¹⁰⁸ Participants rate providers from poor to excellent with a sample item as "Treated me with respect." Communication with caregivers will be measured through several dyadic-based measures. (b) **Satisfaction with care** will be measured with 3 reliable items used by [name] in her prior work.¹⁰⁹ Finally, (c) **Adherence to guideline-concurrent follow-up care** will be based on following care guidelines of the American Society of Clinical Oncology¹¹⁰ and measured using self-report items as done in prior work.¹¹¹

Dyadic Factors. (a) **Dyadic support** will be measured with the 5-item scale by Northouse^{112,113} which assesses the perceived support received by each member of the patient-caregiver dyad. (b) **Dyadic perspective**, meaning considering another's point of view about a specific topic like breast cancer, will be assessed with a modified version of the Thinking Beyond Oneself scale.¹¹⁴ This scale has been used in dyadic cancer control research.⁶³ (c) **Social constraints** will be measured with the 5-item Social Constraints Scale.^{115,116} We have used a Spanish translation of this scale and obtained good internal consistency.²

Process Variables. (a) **Satisfaction.** We will assess satisfaction with PCI and UC. (b) **Intervention fidelity.** We will measure adherence to intervention protocols, participants' engagement (attendance, participation), exposure to intervention content, quality of intervention delivery and differentiation between PCI and UC arms.^{117,118} Staff will complete session contact logs and evaluation forms.¹¹⁸

C.2. Analytic Methods

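### Aim 3's power statement is internally inconsistent: 8 points with an SD of 12 is 0.67 SD, not 0.75 SD, and gives about 91% power with 50 per arm (two-sided 0.05), not 96%

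*Combined protocol and SAP*

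**What the plan says.** The power statement for Aim 3 is in section C.2, Data Analyses. For 50 survivors per arm it claims "96% power to detect a clinically significant difference in satisfaction with care of 8 points (0.75 SD given estimated SD of 12", with reference 120 as the source. The test is "at a significance level of 0.05"; the number of sides is not stated. No correlation, baseline adjustment or other variance reduction is mentioned as part of the calculation. No other section gives a different target difference or SD for satisfaction.

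Two other places bear on the point:

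- Aim 1, in the same section, uses the same 50 per arm and claims "84% power to detect a clinically significant difference in QOL of 6 points (0.6 SD on PROMIS QOL measures". This shows which convention the power calculations follow.
- Section C.1, Secondary Outcomes, says that satisfaction with care "will be measured with 3 reliable items used by" a member of the study team in earlier work (reference 109). It gives no response format, scoring rule or range.

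**The concern.** A raw difference divided by its SD must equal the standardised effect. Here 8 divided by 12 is 0.67, and the line prints 0.75, so at least one of the three numbers is wrong whatever power formula was used.

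The power figure matches the 0.75. A reader who takes the 8 points and the SD of 12 at face value therefore believes that the trial has more power for that difference than it has. A reader who trusts the 0.75 does not know whether the design difference is 8 or 9 points. This matters because the line calls 8 points clinically significant and Aim 3 has its own hypothesis.

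A second, lesser matter is the scale. An SD of 12 has meaning only relative to a score range, and neither the power line nor the description of the three-item measure supplies one.

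**Working it through.** **Inputs.** From Aim 3: n = 50 per arm, difference 8, SD 12, standardised effect 0.75, alpha 0.05, stated power 96%. From Aim 1: n = 50 per arm, standardised effect 0.6, stated power 84%. From the RCT enrolment paragraph of C.2: 125 dyads enrolled, 100 expected to be retained.

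**Method.** Two-sample comparison of means with equal arms. The noncentrality is d × √(n/2), which is 5d at n = 50. Power comes from the noncentral t with 2 × 50 − 2 = 98 degrees of freedom. As a hand check, the normal approximation is Φ(5d − 1.96) for a two-sided test at 0.05.

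**Step 1: reproduce the plan's 96%.** At d = 0.75 the noncentrality is 3.75. Power is 96.0% (t), or Φ(1.79) = 96.3% (normal). The stated figure is reproduced.

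**Step 2: use the printed points and SD.** d = 8/12 = 0.667 and the noncentrality is 3.333. Power is 91.0% (t), or Φ(1.37) = 91.5% (normal). By the t calculation the gap is 96.0 − 91.0 = 5 percentage points.

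**Step 3: check the convention against Aim 1.** At d = 0.6 and 50 per arm, two-sided power is 84.4% (t) and one-sided power is 90.9%. The stated 84% fits the two-sided test, so that is the convention to apply to Aim 3.

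**Step 4: try readings that might rescue 8/12.**

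| Reading | Power at d = 8/12 (t) |
|---|---|
| Two-sided, 50 per arm | 91.0% |
| One-sided, 50 per arm | 95.2% |
| Two-sided, 125/2 = 62.5 per arm (enrolled) | 95.9% |

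The one-sided figure rounds to 95%, not 96%, and departs from Aim 1's convention. The enrolled-sample figure rounds to 96%, but the line itself says 50 per arm. Aim 1 at 62.5 per arm would have 91.4%, not 84%. Neither reading makes 8/12 equal 0.75.

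**Step 5: what would be consistent with 0.75 SD and 96%.** With SD 12 the difference is 0.75 × 12 = 9 points. With 8 points the SD is 8/0.75 = 10.7. Keeping 8 points, SD 12 and 96% power would instead need about 62 analysed survivors per arm (normal approximation).

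**Step 6: can an SD of 12 apply to the outcome?** The SD of a bounded score cannot exceed about half its range. The scorings below are assumptions, because the documents give none.

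| Assumed scoring | Range | Maximum SD | SD of 12 possible? |
|---|---|---|---|
| Three five-point items, summed | 3–15 | 6 | No |
| Three ten-option items, summed | 3–30 | 13.5 | Yes |
| Rescaled score | 0–100 | 50 | Yes |
| The 16 five-option items of Appendix D, Section M, summed 1–5 | 16–80 | 32 | Yes |

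The last row is included because the draft interview prints a medical-care scale there, although nothing identifies it as the Aim 3 outcome. The table shows that the answer depends on unstated scoring. It does not show that 12 is wrong.

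**The case against.** The strongest reply has four parts.

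- **The standardised effect is identifiable.** Since 96% is right for 0.75 SD at 50 per arm, the calculation was evidently run on 0.75, and only its translation into points is in doubt. This is fair and narrows the problem. It does not remove it, because the line presents the raw 8 points as the clinically meaningful quantity.
- **A more efficient analysis could deliver about 96% at 8/12.** With baseline adjustment, an assumed correlation of 0.4 gives 95.3% and 0.5 gives 97.1%. Averaging two follow-ups with an assumed correlation of 0.6 gives 96.1% (all by the normal approximation). The plan states no such assumption, and none of these would turn 8/12 into 0.75.
- **The scoring point is a request for detail, not a demonstrated error.** It rests on two cited sources that are not part of the documents, and Appendix D is a draft that the replication plan describes as incomplete. This stands: the scoring request would not justify a comment alone and carries less certainty than the arithmetic.
- **The consequence is slight.** Satisfaction is secondary, 91% is ample, and a final protocol and written analysis plan are promised in which the line can be corrected. This also stands, and is why the point is minor.

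It is also fair to say that an SD of 10.7 appears nowhere in the documents. It is a back-calculation, whereas 12 carries a citation.

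**Conclusion.** The inconsistency is real. Under a two-sided test at 0.05 with 50 survivors analysed per arm and no variance reduction, the stated 96% belongs to 0.75 SD. The printed 8 points and SD of 12 amount to 0.67 SD and give about 91%. If those two values are the intended ones, power is overstated by 5 percentage points. The mismatch between 8/12 and 0.75 rests on no assumption. The 91% rests on the two-sided convention, which Aim 1's figure supports, and on the sample size in the line itself.

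The documents do not reveal which of the three numbers is the slip. The point is minor: corrected power remains above the 84% stated for the primary outcome, and neither the sample size nor the analysis is threatened. Whether an SD of 12 suits the three-item measure is an open question, not a finding of error.

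**What to change.** Establish which number is wrong from the original calculation and the cited source, and restate the Aim 3 line in one of these forms:

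- 91% power for 8 points (0.67 SD, SD 12);
- 96% power for 9 points (0.75 SD, SD 12);
- 96% power for 8 points (0.75 SD, SD 10.7), only if a source supports that SD.

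State in the line that the test is two-sided. If the difference becomes 9 points, confirm that the description of it as clinically significant still applies.

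Add a sentence giving the response format, scoring and range of the three-item satisfaction measure, and confirm that the SD taken from reference 120 is on that range. The promised final protocol and written analysis plan are the natural places.

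The cost is one corrected line and one added sentence, with no change to sample size or analysis.
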